8.6.3 Laboratory Parameters

Laboratory results will be summarized descriptively for each parameter and dosage group by visit for the observed value as well as for the change from baseline value. Laboratory abnormalities (grade 1 and greater that are listed in the NCI-CTCAE V4.03) will be recorded on the AE page regardless of their causality.

Test analytes are provided in the table below.

Hematology	Serum chemistry
Full and differential blood count	Albumin
Hematocrit (Hct)	Alanine aminotransferase (ALT)
Hemoglobin (Hgb)	Aspartate aminotransferase (AST)
Platelet count	Alkaline phosphatase (ALP)
Red blood cell (RBC) count	Blood Urea Nitrogen (BUN) or Urea
White blood cell (WBC) count with	Carbon dioxide (CO2)
differential	Creatinine
	Electrolytes (Na, K, Cl, Ca, P)
	Glucose (either fasting or non-fasting)
	Lactate dehydrogenase (LDH)
	Total bilirubin
	Direct bilirubin
	Total cholesterol
	Triglycerides
Coagulation, CH50	
Prothrombin time (PT)/INR Activated partial thromboplastin time (PTT)	ALYTICAL

8.6.4 Vital Signs

Vital sign data, including systolic blood pressure (mmHg), diastolic blood pressure (mmHg), temperature (C), and heart rate (bpm), will be summarized descriptively for each dosage group by time point for the observed value as well as for the change from baseline value.

8.6.5 ECOG Performance Score

The health, activity and well-being of the patient is measured by the ECOG performance status and is assessed on a scale of 0 to 5, with 0 being fully active and 5 being dead. The ECOG performance score will be summarized categorically by dosage group and visit. In addition, a shift table will be provided comparing the baseline ECOG

performance score and the worst (highest) post-baseline score that was recorded through Day 43.

8.6.6 ECG

ECG results will be summarized descriptively for each parameter and dosage group by visit for the observed value as well as for the change from baseline value. In addition, a shift table will be provided comparing the baseline overall interpretation (normal, abnormal, not clinically significant, abnormal, clinically significant) to the post-baseline value by visit through Day 43.

8.6.7 Other Safety Variables

Other safety variables, such as physical examination, will be listed.

8.7 Immunological Analysis

All immunological analyses will be conducted on the Immunologic Population.

As for the safety variables, subjects will be summarized through Day 43 using the assigned dose level as the dosage group. For additional treatment visits and end of treatment phase visit, subjects will be summarized by cohort and by the dose level the subject took at the visit immediately prior to the current visit—this allows for subjects who changed their dose level to be summarized at the new (elevated) dose level.

The variables that will be analyzed are listed in Table 8-1:

Туре	Name	Unit
Antigan analifia anti IIA All antihadu titara	ΗΑΑΗ-1λ	Antibody Units / mL
Antigen-specific anti-HAAH antibody titers	H460 (HAAH)	Antibody Units / mL
	CD4+ T Cells IFN-γ	% of CD4+ T cells
Cellular Immune Response	CD8+ T Cells IFN-γ	% of CD8+ T cells
	HAAH-Specific B Cells	% of B cells
	B Cells	% of Leukocytes
	T Cells	% of Leukocytes
	CD4+ T Cells	% of T cells
	CD8+ T Cells	% of T cells
Immunophenotyping	CD3+, CD56+ Cells	% of Leukocytes
1 51 6	NK Cells	% of Leukocytes
	Neutrophils	% of Leukocytes
	Eosinophils	% of Leukocytes
	Monocytes	% of Leukocytes

 Table 8-1.
 Variables Included in Immunological Analysis

Assay data will be tabulated by time point, An appropriate data transformation (e.g., log_{10} transformation) may be applied to better satisfy assumptions of symmetry and homoscedasticity (constant variance). Graphical representations of the longitudinal immune responses will also be given.

All data related to immunologic collection and analysis will be listed.

9 References

10 Appendices

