An evaluation period of at least 21-days for the first patient (sentinel patient) in a new cohort is required to evaluate tolerability before adding additional patients to the cohort. If safety/tolerability is adequate, then the remaining patients will be dosed in the cohort. A second evaluation will occur for the last patient of each cohort of at least 21-days to evaluate safety/tolerability before dose escalation to the next cohort will occur. Enrollment will be held if an administration site reaction (ASR) of grade 3 or greater (NCI-CTCAE V4.03) is observed until the event resolves. In the event enrollment is held for an ASR, the Sponsor, Medical Monitor and PI will evaluate the outcome of the ASR and must agree to continued enrollment.

Dose-escalation will proceed once all patients in a cohort (unless the MTD is observed) have completed a 21-day safety evaluation following the first dose of study treatment in the cohort. Planned treatment may continue for an additional 2 extra doses of SNS-301 administered every 21 days. Additional patients will be enrolled at the highest dose level until at least 6 patients can be evaluated even if no DLTs are observed at the dose. In patients who tolerate SNS-301, additional treatment may be continued with single doses of SNS-301 at their current dose level, to maintain geometric mean titer (GMT) of HAAH antibodies to no less than 4 times the baseline value for at least six months (9 injections). Treatment will be terminated with the 9th injection or will otherwise be terminated at any time upon the observance of PSA doubling < 90 days or occurrence of unacceptable toxicity as determined by the Investigator (either for that patient or in their dose cohort). After termination, patients will be followed for an additional 6 months with monthly PSA levels and imaging studies as needed.

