6.4 Secondary Endpoints

- Incidence of administration site reactions
- Biochemical safety and tolerability (hematology, serum chemistry, coagulation, CH50)
- Geometric mean titers of anti-HAAH antibodies by dose
- Antigen-specific Cytotoxic CD8+ T-lymphocytes (CTL) responses by dose
- Production of B cell and T cell response of interest

Clinical Secondary Endpoints:

- Change in the prostate-specific antigen (PSA) velocity
- Reduction in the PSA doubling time from pre-baseline

Pharmacodynamic Secondary Endpoints:

- Duration of antigen-specific anti-HAAH antibody titers
- Changes in the amplitude or duration of the production of anti-HAAH antibodies
- Correlation of anti-HAAH titers and serum HAAH levels

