14.3.2.6.1	Treatment-Emergent Adverse Events (TEAE) Leading to Permanent Dose Discontinuation by System Organ Class and Preferred Term Through Day 43	Safety

14.3.2.6.2	Treatment-Emergent Adverse Events (TEAE) Leading to Permanent Dose Discontinuation by System Organ Class and Preferred Term For Additional Treatment Visits	Safety
14.3.2.7	Listing of Serious Treatment Emergent Adverse Events	Safety
14.3.3.1.1	Change from Baseline in Hematology Parameters by Visit Through Day 43	Safety
14.3.3.1.2	Change from Baseline in Hematology Parameters by Additional Treatment Visit	Safety
14.3.3.2.1	Change from Baseline in Chemistry Parameters by Visit Through Day 43	Safety
14.3.3.2.2	Change from Baseline in Chemistry Parameters by Additional Treatment Visit	Safety
14.3.3.3.1	Change from Baseline in Coagulation and CH50 Parameters by Visit Through Day 43	Safety
14.3.3.3.2	Change from Baseline in Coagulation and CH50 Parameters by Additional Treatment Visit	Safety
14.3.4.1	Change from Baseline in Vital Sign Parameters by Visit Through Day 43	Safety
14.3.4.2	Change from Baseline in Vital Sign Parameters by Additional Treatment Visit	Safety
14.3.5.1.1	ECOG Performance Score by Visit Through Day 43	Safety
14.3.5.1.2	ECOG Performance Score by Additional Treatment Visit	Safety
14.3.5.2	Shift from Baseline in ECOG Performance Score (Worst Case) Through Day 43	Safety
14.3.6.1.1	Change from Baseline in ECG Parameters by Visit Through Day 43	Safety
14.3.6.1.2	Change from Baseline in ECG Parameters by Additional Treatment Visit	Safety
14.3.6.2	Shift from Baseline in ECG Overall Interpretation by Visit	Safety
14.4.1.1	Summary of Antigen-Specific anti-HAAH Antibody Titers by Visit Through Day 43	Immmunologic
14.4.1.2	Summary of Antigen-Specific anti-HAAH Antibody Titers by Additional Treatment Visit	Immmunologic
14.4.2.1	Summary of Cellular Immune Response by Visit Through Day 43	Immmunologic
14.4.2.2	Summary of Cellular Immune Response by Additional Treatment Visit	Immmunologic
14.4.3.1	Summary of Immunophenotyping by Visit Through Day 43	Immmunologic
14.4.3.2	Summary of Immunophenotyping by Additional Treatment Visit	Immmunologic

Figure No.	Description of Figure	Population
14.4.1.1	Mean (SD) of H460 (HAAH) by Treatment	Immmunologic
14.4.1.2	Mean (SD) of HAAH-1 λ by Treatment	Immmunologic
14.4.2.1	Mean (SD) of CD4+ T Cells IFN-γ by Treatment	Immmunologic
14.4.2.2	Mean (SD) of CD8+ T Cells IFN-γ by Treatment	Immmunologic

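### SAP 8.7 and the 14.4.x outputs specify immune results as values by visit and dose group, with no within-patient change from baseline, although change in antibody amplitude is a listed endpoint

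*SAP*

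**What the plan says.** SAP 6.4 lists two antibody endpoints that matter here: "Geometric mean titers of anti-HAAH antibodies by dose" and, among the pharmacodynamic endpoints, "Changes in the amplitude or duration of the production of anti-HAAH antibodies". The second is by its wording a change.

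SAP 8.7 gives one instruction on how the immune data are summarised: "Assay data will be tabulated by time point". A transformation may be applied, longitudinal graphs are promised and all immune data are listed. The output list in SAP 10.1 follows suit. Table 14.4.1.1 is "Summary of Antigen-Specific anti-HAAH Antibody Titers by Visit Through Day 43", Table 14.4.1.2 is its counterpart for additional treatment visits, and the first figure is "Mean (SD) of H460 (HAAH) by Treatment".

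Other longitudinal data are treated differently. SAP 8.6.3 summarises laboratory results "for the observed value as well as for the change from baseline value". SAP 8.5 (PSA), 8.6.4 (vital signs) and 8.6.6 (ECG) do the same, and the corresponding table titles name the change.

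The ingredients for a change exist. SAP 7.4.5 defines change from baseline in general terms, SAP 7.4.10 defines baseline, and the schedule of assessments takes immunologic blood before the Day 1 dose. Protocol 5.1 also frames continued dosing relative to baseline: "to maintain geometric mean titer (GMT) of HAAH antibodies to no less than 4 times the baseline value".

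**The concern.** An endpoint about change has no specified derivation: neither SAP 8.7 nor any listed 14.4.x table or figure names a change, a fold-rise or a peak. Because four other data types do get change from baseline, this looks like an omission rather than a decision.

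The consequence is for interpretation. Cohorts are small, sequential and not randomised. The protocol introduction describes HAAH as a self-antigen, and patients are selected for expressing it, so pre-dose immunity may differ between patients. A reader who compares dose groups on raw values could take a baseline difference for a response. Immunogenicity is in the trial title and in the SAP's secondary objective, and the protocol synopsis (Dose regimen) allows pharmacodynamic data to bear on the RP2D. These displays are therefore likely to be read for dose.

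**Working it through.** The plan states no SD, correlation, effect size or power for any immune endpoint, so it has no figure to reproduce. The check has four parts.

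**1. Can group summaries by visit stand in for within-patient change?** Take three illustrative patients with baseline titers 25, 50, 100 and post-dose titers 100, 200, 400. The group summaries are fixed: GMT 50 before and 200 after. The pairing is not.
- Folds of 4, 4, 4: three patients reach 4-fold, and the SD of log10 fold is 0.
- Folds of 8, 2, 4: two patients reach it.
- Folds of 16, 2, 2: one patient reaches it.
- Folds of 16, 4, 1: two patients reach it. The log10 folds are 1.204, 0.602 and 0, with SD 0.602.

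The geometric mean fold-rise is 4.0 in every case. The centre of the change is recoverable from GMTs when data are complete; its spread and the individual rises are not.

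**2. Can raw post-dose values mislead across doses?** Give one cohort a baseline GMT of 50 and another 100, each with a uniform 4-fold rise. Post-dose GMTs are 200 and 400, a 2-fold gap, while the fold-rises are 4.0 and 4.0.

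**3. How large could a chance baseline gap be?** Assume independent patients, normal log10 titers and equal true baselines. The SE of the difference in mean log10 titer is SD × sqrt(1/n1 + 1/n2), and P(gap of at least k-fold) = 2 × [1 − Phi(log10 k / SE)]. The SD is an assumption, so a range is shown.

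For 3 vs 3 patients and a gap of at least 4-fold (log10 4 = 0.602):

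| Assumed SD (log10) | SE | SE as a fold | P(gap at least 4-fold) |
|---|---|---|---|
| 0.3 | 0.245 | 1.8 | 1% |
| 0.5 | 0.5 × sqrt(2/3) = 0.408 | 2.6 | 14% |
| 0.7 | 0.572 | 3.7 | 29% |

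For a gap of at least 2-fold:

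| Assumed SD (log10) | 3 vs 3 | 3 vs 6 | 6 vs 6 |
|---|---|---|---|
| 0.2 | 7% | 3% | 1% |
| 0.3 | 22% | 16% | 8% |
| 0.4 | 36% | 29% | 19% |
| 0.6 | 54% | 48% | 38% |

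**4. What does change from baseline gain or lose?** With equal variance at both times and within-patient correlation rho, Var(change) / Var(raw value) = 2(1 − rho). The ratio is 0.6 at rho 0.7, 1.0 at rho 0.5 and 1.4 at rho 0.3. At SD 0.5 and 3 vs 3, the SE of the difference becomes 0.408 × sqrt(2(1 − rho)):
- rho 0.7: SE 0.316, and a spurious gap of at least 4-fold has probability 6%.
- rho 0.5: SE 0.408, 14%, the same as for raw values.
- rho 0.3: SE 0.483, 21%, worse than raw values.

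A 95% confidence interval for the mean log10 change at n = 3, SD 0.5 and rho 0.7 has half-width 4.30 × 0.387 / sqrt(3) = 0.96, about 9-fold each way.

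**The case against.** Several points on the other side are sound.

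- **The outputs may contain a change.** SAP 7.4.5 defines one study-wide, and the table shells are in a separate document that is not available here. A reader might infer that change will never be computed. The documents do not show that; they show that it is not specified in SAP 8.7 or in the output titles. The derivation of a listed endpoint still belongs in the SAP.
- **Baseline is not hidden.** Day 1 is a visit, so the through-Day 43 tables should show it by dose group. With complete data on the log scale, the ratio of GMTs equals the geometric mean fold-rise. This stands through Day 43. It weakens afterwards, when patients are summarised by cohort and by the dose taken at the preceding visit, in separate tables. The Immunologic Population in SAP 5 also requires follow-up data but no baseline sample, so the patients behind each row can differ.
- **No dose comparison is planned.** Protocol 6.1 rules out formal analysis and has the data shown for inspection; SAP 8.7 names no contrast or test. A reader might infer that a planned comparison is biased. None exists, so the probabilities above describe what inspection might show, not the error rate of a decision. DLTs determine the MTD.
- **The 4-times-baseline text is not a responder definition.** A reader might treat it as a patient-level target that the plan fails to count. It is worded as a GMT to be maintained by continued dosing, and no responder endpoint is listed.
- **Baselines may be uniform.** The protocol says tolerance makes anti-HAAH responses hard to elicit, which fits uniformly low baselines. Raw values and fold-rises would then rank doses alike.
- **The endpoint covers antibody only**, two of the 14 variables in SAP Table 8-1. For the other 12 the case rests on consistency with other sections.

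**Conclusion.** The specification gap is real. SAP 6.4 lists change in antibody amplitude, and neither SAP 8.7 nor the 14.4.x list says how a change will be derived or shown. By-visit group summaries do not replace it, least of all after the post-Day 43 regrouping.

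The size of any misreading cannot be fixed from the documents. It rests on an assumed titer SD and correlation, and the chance of a 4-fold baseline gap between cohorts of 3 runs from 1% to 29% for SDs of 0.3 to 0.7. The effect is on descriptive interpretation, not on the MTD or any planned test. The point is worth correcting because the remedy is nearly free, not because the harm is shown to be large.

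**What to change.** In SAP 8.7 and Tables 14.4.1.1 and 14.4.1.2, for the two antibody variables:
- Add the within-patient log10 change from the Day 1 pre-dose value, reported as geometric mean fold-rise with individual values or range, by visit and dose group, beside the raw values.
- Base it on patients with a Day 1 value, and show baseline for the same patients in every row, including after Day 43.
- Plot individual profiles.

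Optional additions:
- Simple change from baseline for the cellular variables, to match SAP 8.5 and 8.6.
- A count of patients with at least a 4-fold rise, labelled exploratory because the protocol's wording refers to the GMT.
- Confidence intervals, which would be uninformative at n = 3.

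The cost is SAP wording and a few columns; the Day 1 sample is already scheduled. The downside is that change is noisier than the raw value when within-patient correlation is below 0.5, which is why both should be shown.

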10.1 List of Tables, Figures, and Listings

Table No.	Description of Table	Population
4.1.1	Subject Disposition	All Subjects
4.1.2.1	Demographics and Baseline Characteristics	Safety
14.1.2.2	Demographics and Baseline Characteristics	Immunologic
14.2.1.1	Study Treatment Administration Through Day 43	Safety
14.2.1.2	Study Treatment Administration by Additional Treatment Visit	Safety
14.2.2.1	Concomitant Medications Through Day 43	Safety
14.2.2.2	Concomitant Medications For Additional Treatment Visits	Safety
14.2.3.1.1	Change from Baseline in PSA by Visit Through Day 43	Safety
4.2.3.1.2	Change from Baseline in PSA by Additional Treatment Visit	Safety
14.2.3.2.1	Summary of PSA Velocity and PSA Doubling Time Through Day 43	Safety
14.2.3.2.2	Summary of PSA Velocity and PSA Doubling Time Through End of Treatment	Safety
14.2.3.2.3	Summary of PSA Velocity and PSA Doubling Time Through End of Study	Safety
14.3.1.1.1	Summary of Worst Administration Site Reactions Through Day 43 by Grade	Safety
14.3.1.1.2	Summary of Worst Administration Site Reactions For Additional Treatment Visits by Grade	Safety
14.3.1.2.1	Summary of Administration Site Reactions by Visit Through Day 43 and Grade	Safety
14.3.1.2.2	Summary of Administration Site Reactions by Additional Treatment Visit and Grade	Safety
14.3.2.1.1	Overall Summary of Adverse Events Through Day 43	Safety
14.3.2.1.2	Overall Summary of Adverse Events For Additional Treatment Visits	Safety
14.3.2.2.1	Treatment-Emergent Adverse Events (TEAE) by System Organ Class and Preferred Term Through Day 43	Safety
14.3.2.2.2	Treatment-Emergent Adverse Events (TEAE) by System Organ Class and Preferred Term For Additional Treatment Visits	Safety
14.3.2.3.1	Treatment-Emergent Adverse Events (TEAE) by System Organ Class and Severity Through Day 43	Safety
14.3.2.3.2	Treatment-Emergent Adverse Events (TEAE) by System Organ Class and Severity For Additional Treatment Visits	Safety
14.3.2.4.1	Treatment-Emergent Adverse Events (TEAE) by Preferred Term and Relationship to Study Treatment Through Day 43	Safety
4.3.2.4.2	Treatment-Emergent Adverse Events (TEAE) by Preferred Term and Relationship to Study Treatment For Additional Treatment Visits	Safety
4.3.2.5.1	Serious Treatment-Emergent Adverse Events (TEAE) by System Organ Class and Preferred Term Through Day 43	Safety
4.3.2.5.2	Serious Treatment-Emergent Adverse Events (TEAE) by System Organ Class and Preferred Term For Additional Treatment Visits	Safety
14.3.2.6.1	Treatment-Emergent Adverse Events (TEAE) Leading to Permanent Dose Discontinuation by System Organ Class and Preferred Term Through Day 43	Safety

14.3.2.6.2	Treatment-Emergent Adverse Events (TEAE) Leading to Permanent Dose Discontinuation by System Organ Class and Preferred Term For Additional Treatment Visits	Safety
14.3.2.7	Listing of Serious Treatment Emergent Adverse Events	Safety
14.3.3.1.1	Change from Baseline in Hematology Parameters by Visit Through Day 43	Safety
14.3.3.1.2	Change from Baseline in Hematology Parameters by Additional Treatment Visit	Safety
14.3.3.2.1	Change from Baseline in Chemistry Parameters by Visit Through Day 43	Safety
14.3.3.2.2	Change from Baseline in Chemistry Parameters by Additional Treatment Visit	Safety
14.3.3.3.1	Change from Baseline in Coagulation and CH50 Parameters by Visit Through Day 43	Safety
14.3.3.3.2	Change from Baseline in Coagulation and CH50 Parameters by Additional Treatment Visit	Safety
14.3.4.1	Change from Baseline in Vital Sign Parameters by Visit Through Day 43	Safety
14.3.4.2	Change from Baseline in Vital Sign Parameters by Additional Treatment Visit	Safety
14.3.5.1.1	ECOG Performance Score by Visit Through Day 43	Safety
14.3.5.1.2	ECOG Performance Score by Additional Treatment Visit	Safety
14.3.5.2	Shift from Baseline in ECOG Performance Score (Worst Case) Through Day 43	Safety
14.3.6.1.1	Change from Baseline in ECG Parameters by Visit Through Day 43	Safety
14.3.6.1.2	Change from Baseline in ECG Parameters by Additional Treatment Visit	Safety
14.3.6.2	Shift from Baseline in ECG Overall Interpretation by Visit	Safety
14.4.1.1	Summary of Antigen-Specific anti-HAAH Antibody Titers by Visit Through Day 43	Immmunologic
14.4.1.2	Summary of Antigen-Specific anti-HAAH Antibody Titers by Additional Treatment Visit	Immmunologic
14.4.2.1	Summary of Cellular Immune Response by Visit Through Day 43	Immmunologic
14.4.2.2	Summary of Cellular Immune Response by Additional Treatment Visit	Immmunologic
14.4.3.1	Summary of Immunophenotyping by Visit Through Day 43	Immmunologic
14.4.3.2	Summary of Immunophenotyping by Additional Treatment Visit	Immmunologic

Figure No.	Description of Figure	Population
14.4.1.1	Mean (SD) of H460 (HAAH) by Treatment	Immmunologic
14.4.1.2	Mean (SD) of HAAH-1 λ by Treatment	Immmunologic
14.4.2.1	Mean (SD) of CD4+ T Cells IFN-γ by Treatment	Immmunologic
14.4.2.2	Mean (SD) of CD8+ T Cells IFN-γ by Treatment	Immmunologic
14.4.2.3	Mean (SD) of HAAH-Specific B Cells by Treatment	Immmunologic
14.4.3.1	Mean (SD) of B Cells by Treatment	Immmunologic
14.4.3.2	Mean (SD) of T Cells by Treatment	Immmunologic
14.4.3.3	Mean (SD) of CD4+ T Cells by Treatment	Immmunologic
14.4.3.4	Mean (SD) of CD8+ T Cells by Treatment	Immmunologic
14.4.3.5	Mean (SD) of CD3+, CD56+ Cells by Treatment	Immmunologic
14.4.3.6	Mean (SD) of NK Cells by Treatment	Immmunologic
14.4.3.7	Mean (SD) of Neutrophils by Treatment	Immmunologic
14.4.3.8	Mean (SD) of Eosinophils by Treatment	Immmunologic

9	Mean (SD) of Monocytes by Treatment Immmunol
Listing No.	Description of Listing
16.2.1.1	Subject Disposition
16.2.1.2	End of Treatment
16.2.1.2	Treatment Assignment and Analysis Populations
16.2.1.3	Elgibility
16.2.2.1	Protocol Deviations
16.2.2.2	Demographics
16.2.2.3	Oncology History
16.2.2.4	General Medical History
16.2.2.5	Tumor Burden Evaluation
16.2.3	Study Treatment Administration
16.2.4	Prior and Concomitant Medications
16.2.5	Immunological Results
16.2.6	Physician Administration Site Assessment
16.2.7	Adverse Events
16.2.8.1	Laboratory Results – Hematology and Coagulation
16.2.8.2	Laboratory Results – Chemistry and PSA
16.2.8.3	Laboratory Results – CH50
16.2.8.4.1	PSA Velocity and PSA Doubling Time Through Day 43
16.2.8.4.2	PSA Velocity and PSA Doubling Time Through End of Study
16.2.9	ECOG Performance Score
16.2.10.1	ECG Parameters
16.2.10.2 16.2.11	ECG Overall Interpretation Vital Signs
16.2.12	Physical Examination

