7.4 Analysis of the Study

All statistical tests will be two-sided and a difference resulting in a p-value of less than or equal to 0.05 will be considered statistically significant. All p-values will be rounded to and displayed in four decimals. If a p-value less than 0.0001 occurs it will be shown in tables as <0.0001.

There will be no multiplicity adjustments.

Descriptive summaries of variables will be provided where appropriate. For continuous variables, the number of non-missing values (n) and the median, mean, standard deviation, minimum, and maximum will be tabulated by dosage group. For categorical variables, the counts and proportions of each value will be tabulated by dosage group. Since this study allows for subjects to change their dose level during additional treatment visits after Day 43, the dose level can change over the course of the study; see Section 8 for how summaries by dosage group will be handled when dose levels vary.

Expansion of descriptive table categories within each treatment may occur if such elaborations are thought to be useful.

Assessments completed during the 6-month follow up period after study treatment will not appear in any tables or graphs (unless noted otherwise), but will be included in the data listings, classified under the last dose level the subject took at the last treatment visit prior to the end of study.

All collected data will be presented in listings. Data not subject to analysis according to this plan will not appear in any tables or graphs but will be included in the data listings.

Post-hoc exploratory analyses not identified in this SAP may be performed to further examine the study data. These analyses will be clearly identified as such in the final clinical study report.

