8.5 Clinical Analysis

PSA will be summarized descriptively for each dosage group by visit for the observed value as well as for the change from baseline value (Day 1). Subjects will be summarized through Day 43 using the assigned dose level as the treatment group. For additional treatment visits, follow up visits, and end of study, subjects will be summarized by cohort and by the dose level the subject took at the visit immediately prior to the current visit—this allows for subjects who changed their dose level to be summarized at the new dose level.

PSA velocity (ng/mL/year) will be estimated by the slope of the least-square regression line fit to PSA versus time in years [1]. PSA velocity will be calculated using PSA values between Day 1 and Day 43, and subjects will be summarized using the assigned dose level as the treatment group. Also, to account for additional treatment visits, PSA velocity will be calculated using PSA values between Day 1 and the end of treatment phase visit, and subjects will be summarized by cohort and by the dose level the subject took at the last additional treatment visit. Finally, to account for follow up visits, PSA velocity will be calculated using PSA values between Day 1 and the end of study visit, and subjects will be summarized by cohort and by the dose level the subject took at the last treatment visit prior to the end of study.

PSA doubling time (months) will be estimated as follows for each visit range [1]:

- 1) Calculate the natural log-transform of all PSA observations [log(PSA)] in the visit range
- 2) Determine the slope of the least-square regression line of log(PSA) versus time in months of PSA measurement; convert the slope from years to months by multiplying the slope in years by the factor 12.
- 3) Divide the natural log of 2 [log(2)] by the slope calculated in step 2.

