PSA doubling time will be estimated for 3 visit ranges: 1) up to and including Day 1 (baseline); 2) Day 1 through Day 43; 3) Day 1 through end of treatment phase visit; and 4) Day 1 through end of study. The baseline value will use all PSA values collected in the Medical History eCRF as well as any screening or Day 1 values in the safety laboratory data extract. For each post-baseline date range, each subject's PSA doubling time will be compared to their baseline value, and the number of subjects who have improved in the parameter (longer or negative doubling time) will be summarized, as well as the number of subjects who have not improved or who are worse (no change or shorter doubling time). For the summary from Day 1 through Day 43, subjects will be summarized using the assigned dose level as the treatment group. For Day 1 through end of treatment phase visit, subjects will be summarized by cohort and by the dose level the subject took at the last additional treatment visit and for Day 1 through end of study, subjects will be summarized by cohort and by the dose level the subject took at the last additional treatment visit and for Day 1 through end of study, subjects will be summarized by cohort and by the dose level the subject took at the last additional treatment visit and for Day 1 through end of study.

All PSA analyses will be conducted on the Safety Population.

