10.2 Mock Tables, Figures, and Listings

Please refer to the separate document of table, figure, and listing shells and programming notes.

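### PSA doubling time is left under the SAP's default mean, SD and median, with no rule for zero or near-zero slopes, although ln 2/slope breaks at zero and is negative for falling PSA

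*SAP*

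**What the plan says.** SAP Section 8.5 regresses log PSA on time for each subject and then instructs: "Divide the natural log of 2 [log(2)] by the slope calculated in step 2". It does so for a baseline window and three post-baseline windows: Day 1 to Day 43, to the end of the treatment phase, and to the end of study. The one summary of doubling time that it describes is a count against each subject's own baseline: "the number of subjects who have improved in the parameter (longer or negative doubling time) will be summarized", alongside the number who did not improve or got worse.

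The general rule is in SAP Section 7.4. It opens with "Descriptive summaries of variables will be provided where appropriate" and continues: "For continuous variables, the number of non-missing values (n) and the median, mean, standard deviation, minimum, and maximum will be tabulated by dosage group".

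SAP Section 10.1 lists Tables 14.2.3.2.1 to 14.2.3.2.3, the first being "Summary of PSA Velocity and PSA Doubling Time Through Day 43". The titles name no statistic. Section 10.2 sends the reader elsewhere for the layouts: "Please refer to the separate document of table, figure, and listing shells and programming notes".

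Neither section takes doubling time out of the default set, and neither says how to treat a slope that is zero or close to it.

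**The concern.** Doubling time is the reciprocal of an estimated slope, so it is not an ordered scale. As a slope shrinks towards zero from above, doubling time runs to plus infinity; just below zero it restarts at minus infinity. Two patients with almost identical flat PSA can therefore sit at opposite ends of the scale. A falling PSA, the best outcome, gives a negative number that pulls a mean down and sorts below every short doubling time in a median.

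The change in doubling time is a named clinical secondary endpoint (Protocol 4.2.3, SAP 6.4), and cohorts have 3 or 6 patients. One near-flat patient can set the cohort mean. A cohort in which some patients stabilise or improve can then show a shorter, or negative, average doubling time.

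**Working it through.** The plan gives no doubling-time figure to reproduce, so the check is of how the statistic behaves.

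**Inputs from the documents.** Doubling time = ln 2/slope (SAP 8.5). Cohorts of 3 or 6 (SAP 7.1). PSA at Days 1, 22 and 43, then every 21 days to the 9th dose, then every 28 days for 6 months (schedule of events). This gives 3 values to Day 43, 10 through end of treatment (9 dose visits plus the first follow-up visit) and 15 through end of study (9 plus 6). Entry excludes doubling times under 3 months; under 12 months is one of three alternative entry criteria. I use 9 months as the main case.

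**Assumed.** Within-patient PSA CV of 5%, 10% and 15%, which the documents do not give, with normal error on the log scale. Time is in months.

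**1. The break at zero.** Slope +0.001 per month: 0.693/0.001 = +693 months. Slope -0.001: -693 months.

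**2. One patient, Day 43 window, CV 10%.**
- Visits at 0, 0.69 and 1.38 months: Sxx = 2 × 0.69² = 0.952.
- SD on the log scale = √ln(1 + 0.10²) = 0.0998. SE of slope = 0.0998/√0.952 = 0.102 per month.
- True slope = 0.693/9 = 0.0770. z = 0.0770/0.102 = 0.75, so about 23% of fitted slopes are at or below zero although PSA is rising.

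**3. Cohorts, Day 43 window.** 200,000 simulated cohorts per setting, each fitted slope drawn from Normal(true slope, SE), every true doubling time 9 months:

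| n | CV | mean DT < 0 | median DT < 0 | mean slope < 0 |
|---|---|---|---|---|
| 6 | 5% | 15% | 0.5% | <0.1% |
| 6 | 10% | 31% | 12% | 3% |
| 6 | 15% | 37% | 22% | 11% |
| 3 | 10% | 30% | 13% | 10% |
| 3 | 15% | 37% | 22% | 19% |

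At n = 6 and CV 10%, the 5-95% range of the cohort mean is about -36 to 44 months. Other true values at the same n and CV give a negative mean in 22% of cohorts (6 months) and 36% (12 months). Going from 3 to 6 patients does not help.

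**4. Longer windows, all patients rising, full schedule.** At 9 months and CV 5-15%, the mean is negative in at most 0.3% of cohorts through end of treatment and in none through end of study. The worst setting tried (12 months, CV 20%, n = 6) gave 9% through end of treatment and still none through end of study.

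**5. Longer windows, mixed cohorts.** No noise is needed:
- 9, 9, 9, 9, -24, -24: mean = (36 - 48)/6 = -2 months. Mean slope = ln 2 × (4/9 - 2/24)/6 = 0.0417 per month, and ln 2/0.0417 = 16.6 months.
- 9, 9, 9, -24, -24, -24: median = (-24 + 9)/2 = -7.5 months.

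With noise at CV 10% and n = 6, four patients at 9 months and two truly flat give a negative mean in 41% of cohorts (end of treatment) and 45% (end of study). Three at 9 months and three halving every 24 months give 91% and over 99%. The mean slope is essentially never negative in these cases.

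**The case against.** The strongest reply is that no sentence in the SAP says doubling time will be reported as a mean. That stands. A reader might infer it from the table titles, but they name no statistic. It follows only from the Section 7.4 default, which is qualified by appropriateness, and the shells are in a document not available here. They may already omit it. Still, the qualifier does not tell a programmer which variables to leave out, and the same tables carry PSA velocity, for which the default is natural.

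Second, the one doubling-time summary that Section 8.5 does describe treats sign properly, because "longer or negative doubling time" counts as improvement. That also stands, and the count is the specified comparison with baseline. It does not replace the default statistics.

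Third, the default set includes the median, which is less affected: negative in 12% of Day 43 cohorts against 31% for the mean (n = 6, CV 10%). This is true, but the median is still misordered when several patients fall.

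Fourth, the remedy is not free of the problem. ln 2 over the mean slope has the same break at zero and is negative in 3% (n = 6) to 10% (n = 3) of Day 43 cohorts at CV 10%. This stands and has to be stated with the fix.

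Fifth, the trial is a Phase I study with no formal analysis (Protocol 6.1), and individual values are listed, so a reader could spot an outlier. That limits the harm but does not make the summary row correct.

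**Conclusion.** The gap is real: doubling time is not exempted from the default mean, SD and median, and there is no rule for slopes at or near zero. Its effect depends on the window.

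In the Day 43 table, a negative cohort mean with every PSA truly rising is a realistic risk: about 15-37% of cohorts at n = 6, a true doubling time of 9 months and an assumed CV of 5-15%. A reader might extend this to all three tables. The documents' visit schedule does not support that: with full attendance the all-rising case is at most 0.3% in the later windows under the same assumptions. Patients who stop early have fewer values and a higher risk. In the later windows the failure comes from flat or falling patients, which is what a working treatment would produce.

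Nor can one conclude that the endpoint as a whole points the wrong way, since the improved/not-improved count has the sign right.

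The size rests on the assumed CV; the break at zero and the worked averages do not. This should be corrected, as a matter of presentation for a descriptive secondary endpoint.

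**What to change.** In SAP Section 8.5 and the shells for Tables 14.2.3.2.1 to 14.2.3.2.3:

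- Exempt PSA doubling time from the Section 7.4 mean, SD and median.
- Summarise the log-PSA slope per month (mean, SD, median, 95% CI) and its change from baseline, by dosage group and window.
- Show doubling time as individual values in the listings. Section 10.1 has listings for Day 43 and end of study; add one for end of treatment.
- At group level, give doubling time only as ln 2/(mean or median slope) when that slope is positive, and otherwise print 'not doubling'. Report the number of subjects with slope at or below zero.
- Keep the improved/not-improved count as it is.
- Footnote the Day 43 table: three PSA values leave group estimates imprecise, and even ln 2/(mean slope) would be negative in roughly 3% (n = 6) to 10% (n = 3) of cohorts at an assumed CV of 10% and a true doubling time of 9 months.

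The cost is SAP wording, table shells and one listing. The slopes are already computed in Section 8.5, step 2, so no new data are needed.
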